3.3 MEDICAL HISTORY AND CONCOMITANT DISEASES

3.3.1 Available data

Medical history findings are coded using the medical dictionary for regulatory activities (MedDRA) into system organ classes (SOC) and preferred terms (PT). For

each finding, a start and stop date or ongoing flag is collected. The MedDRA version will be updated to the latest one until the database lock of 2009.

3.3.2 Derivation rules

Medical history finding: not ongoing at screening, ended before date of signing informed consent.

Concomitant disease: medical history condition still ongoing at screening.

3.3.3 Presentation of results

Medical history and concomitant diseases will be tabulated separately. Both tables will show:

- · The number and percentage of participants with findings
- The number and percentage of participants with findings by SOC and PT

All medical history (not ongoing at screening) and concomitant disease (still ongoing at screening) data will be listed.

3.4 PRIOR AND CONCOMITANT THERAPIES AND PROCEDURES

3.4.1 Available data

Following therapies are collected in the CRF:

- BP therapy history (until baseline)
- Vaccination history
- OCS administration
- Prior and concomitant therapies, including BP rescue therapies
- Procedures

[figure not shown]
All therapies are coded using World Health Organization Drug Dictionary (WHO DD). Anatomical-Therapeutic-Chemical (ATC) selection is performed to select the most appropriate medication class. For the selected class, ATC coding up to level 4 is available in the clinical database. For each therapy, a start date or prior flag and stop date or ongoing flag are collected.

Procedures are coded using the medical dictionary for regulatory activities (MedDRA) into preferred terms. For each finding, the indication and a start and stop date are collected.

3.4.2 Derivation rules

Based on their start and stop dates, therapies will be allocated to each phase and period during which the participant received the therapy.

Therapies/procedures with (partially) missing dates will be allocated to each phase/period unless the available parts of the therapy/procedure start or stop date provide evidence not to do so.

Based on their start and stop date, therapies and procedures will be allocated into one or both of the following categories:

- Prior: any therapy/procedure that strictly started before the first IMP.
- Concomitant: any therapy/procedure that was taken on or after the first IMP.

A medication that started before the first IMP and continued during the study will be classified as both prior and concomitant.

Therapies/procedures with (partially) missing dates will be allocated to each category unless the available parts of the therapy/procedure start or stop date provide evidence not to do so.

Under certain conditions (see CTP section 6.8.3), participants will discontinue IMP treatment and may start rescue therapy. Rescue therapy may include OCS, TCS, immunosuppressants, tetracyclines with or without nicotinamide, dapsone, or IVIg.

Intercurrent events (ICE) of disallowed therapies that may influence efficacy are defined as any of the following therapies (and that are not prescribed as rescue therapy):

- Immunosuppressants or dapsone at therapeutic doses for at least 4 weeks in total
- IVIg /SCIg at immunomodulating dose (≥1 g/kg/month)
- Tetracyclines at therapeutic dose for at least 2 weeks in total
- Rituximab or other anti-CD20 biologics, at least 1 infusion
- Plasma exchange or Immunoadsorption, at least 1 procedure
- IV or IM corticosteroids

At least 1 administration, any dose, from week 28 to 36 (i.e., during the 8-week period required to confirm CR off OCS therapy) or

At any time before week 28 in any of the 3 following situations:

- More than 60 mg/day of prednisone or prednisone equivalent dose for 3 consecutive days
- More than 40 mg/day of prednisone or prednisone equivalent dose for 4 consecutive days
- More than 7 days in total
- Any interventional study drugs under development for BP
- Very potent topical corticosteroids (TCS) for 7 consecutive days or 14 days in total

Note: if dose is missing and/or period of intake cannot be derived, it is still considered an intercurrent event.

Details on the derivation of intercurrent events are provided in appendix 9.1. More information how these intercurrent events are handled can be found in the efficacy section 4.1.

SGS	Statistical Analysis Plan	
ARGX-113-2009	Final and Interim Analysis	Final 4.0 of 04NOV2024

3.4.3 Presentation of results

Therapies will be tabulated by ATC class (level 1 and 3) and generic term. Tables will be created for:

- Prior therapies (excluding therapies from the BP history CRF form)
- BP therapy history (all therapies from the BP history CRF form)
- Concomitant therapies (excluding medications from the OCS CRF form, excluding rescue therapies and excluding disallowed therapies that classify as intercurrent event)
- Concomitant OCS and equivalent medications administered for BP (all medications from the OCS CRF form, excluding OCS medications administered as rescue therapy)
- Rescue therapies (excluding medications from the OCS CRF form)
- Disallowed therapies that classify as intercurrent event (excluding rescue therapies)

Concomitant therapies and concomitant OCS therapies will be tabulated for the on IMP treatment period, off IMP treatment period, and FU phase separately.

All prior and concomitant therapies/procedures data will be listed with detailed information about ATC classes. Furthermore, separate listings will be created for BP therapy history, rescue therapies and for disallowed therapies that classify as intercurrent event.

3.5 IMP AND OCS ADMINISTRATION

3.5.1 Available data

For each IMP administration and OCS administration, the start and end date, doses (per administration), dose units and the volume with units (for IMP only) will be recorded.

3.5.2 Derivation rules

Normalized cumulative OCS dose (NCOD) will be calculated based on prednisone equivalent doses. Prednisone equivalent dose is calculated as [dose of ATC]*[equivalence factor prednisone]/[equivalence factor ATC]. Following [equivalence factors] are used:

ARGX-113-2009

Statistical Analysis Plan

Final and Interim Analysis

Final 4.0 of 04NOV2024

- Betamethasone [1.5]
- Cortisone [37.5]
- Deflazacort [15]
- Dexamethasone [1.5]
- Fluocortolone [10]
- Hydrocortisone [30]
- Hydrocortisone sodium phosphate [30]
- Methylprednisolone [8]
- Methylprednisolone acetate [8]
- Methylprednisolone sodium succinate [8]
- Paramethasone [4]
- Prednisolone [10]
- Prednisone [10]
- Prednisolone acetate [10]
- Prednisone acetate [10]
- Prednisolone sodium succinate [10]
- Prednylidene [12]
- Rimexolone [20]
- Triamcinolone [8]

[figure not shown]
Example: calculation of equivalent dosage of 12 mg methylprednisolone: 12*10/8= 15 mg prednisone.

Only systemic use of oral medication is included.

NCOD (mg/kg/day) is calculated for different periods as [the sum of (equivalent doses taking into account daily dose frequency)/(body weight in kg)]/(period duration in days) with body weight of visit closest before or at each intake of OCS medication. If for a given day of analysis period, no record exists in the CRF indicating OCS use that day, the dose will be assumed to be 0 mg. NCOD will be calculated with and without considering main intercurrent events (see efficacy section 4.1.3.1). Additionally, the cumulative OCS dose (COD, in mg) over these periods will be calculated.

The denominator of the NCOD should cover all days on IMP treatment in the study, starting at baseline. Following periods are considered (including start and end of the period):

- Over the whole 2009 on IMP treatment period
- From first IMP administration until CDA or end of on IMP treatment period (whichever comes first)
- From first IMP administration until CR or end of on IMP treatment period (whichever comes first)

- From first IMP administration until CR while on minimal OCS therapy for ≥8 weeks or end of on IMP treatment period (whichever comes first)
- From first IMP administration until CR/PR while off OCS therapy for ≥8 weeks or end of on IMP treatment period (whichever comes first)
- From first IMP administration until CR while off OCS therapy for ≥8
 weeks or end of on IMP treatment period (whichever comes first)
- From CDA onset until Relapse or end of on IMP treatment period (whichever comes first) (Only defined on the subset of participants that achieve CDA during the on IMP treatment period)
- From CR onset until Relapse or end of on IMP treatment period (whichever comes first) (Only defined on the subset of participants that achieve CR during the on IMP treatment period)

Details on how to derive the time till CDA, CR, CRmin, CR/PRoff and CRoff are included in section 4.1.4.

Following rules will be applied to allocate OCS administrations to the correct period:

- Only the start and stop date information will be considered
- Records with (partially) missing dates will be imputed as detailed in section 2.3.2.
- If dates of administration records overlap, the reported doses will be added together.
- If an administration is reported as dose per administration with frequency, then the doses should be allocated to the correct dates, taking the start date and the frequency into account. Example:
 - O Dose: 40 mg
 - Frequency: every other day
 - o Start Stop date: 01JAN2022 03JAN2022

[figure not shown]
This will result in:

- o 40 mg be allocated to 01JAN2022
- o 0 mg allocated to 02JAN2022
- o 40 mg allocated to 03JAN2022

The following parameters will be derived for IMP administration:

- Number of administrations: sum of all administrations of study drug.
 Two administrations are expected on day 1 and day 8.
- Number of loading doses: i.e., daily doses of 2000 mg (2 administrations of 1000 mg).

The following parameters will be derived for IMP self-administration by participant and by caregiver:

- Number of participants/caregivers receiving the self-administration training.
 - Number of training visits received by participant/caregiver.
- Number of participants/caregivers who were adequately trained and capable to self-administer efgartigimod.
- Number of training visits before being considered capable to selfadminister.

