2.2 PHASES AND TIME POINTS

2.2.1 Analysis phases

All events and assessments will be allocated to phases as defined below.

[figure not shown]

Table 1: Phase and period definition

Phase	Period	Start	End ^[2]
Screening		Date of signing the informed consent form (ICF), with 00:00 added as time part	First IMP administration date/time – 1 minute
Treatment [1]	On IMP treatment	First IMP administration date/time	Last IMP administration date with 23:59 added as time part.
			For participants with ongoing treatment at the time of the interim analysis, date of database cut-off with 23:59 added as time part.
	Off IMP treatment	End of on IMP treatment period + 1 minute	For participants who roll-over to study 2010, date of trial termination (of study 2009), with 23:59 added as time part.
			For participants who do not roll-over to study 2010 and have an EoTP visit: date of EoTP visit, with 23:59 added as time part.
			For participants who do not roll-over to study 2010 and have no EoTP visit, date of trial termination (of study 2009), with 23:59 added as time part.
			For participants ongoing in the study at the time of the interim analysis, date of database cut-off with 23:59 added as time part.
Following ph over to study		plicable for participants who had	the EoTP visit and who do not roll-
Follow-up (FU)		End of treatment phase + 1 minute	Date of trial termination (of study 2009), with 23:59 added as time part.
			For participants ongoing in the study at the time of the interim analysis, date of database cut-off with 23:59

Although the baseline falls within the Screening phase, it will be allocated to the Treatment phase in ADaM.

End of the treatment phase is the maximum of the end of the on IMP treatment period and off IMP treatment period.

added as time part.

Adverse events will be allocated to phases as described in section 5.1.2. Concomitant medications will be allocated to phases and periods as described in section 3.4.2. All other assessments will be allocated to phases based on the assessment date/time.

In case of (partially) missing date/time fields disabling allocation, information from the visit label and the protocol schedule of activities will be used to allocate to the correct phase. If this is not possible, assessments will be allocated to the treatment

SGS	Statistical Analysis Plan	
ARGX-113-2009	Final and Interim Analysis	Final 4.0 of 04NOV2024

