4.1.3.1 HANDLING OF INTERCURRENT EVENTS, RESCUE THERAPY AND MISSING DATA

1) Normalized cumulative OCS dose (NCOD, mg/kg/day) over the on IMP treatment period.

Main intercurrent events are defined as follows, and handled in a 'while on treatment' strategy:

• Intercurrent medications (see section 3.4.2): stop calculating cumulative dose after ICE. In case 'immunosuppressants for at least 4 weeks in total' is the ICE, use end of the 4 weeks IC medication as stop for cumulative dose calculation. In case 'tetracyclines for at least 2 weeks in total' is the ICE, use end of the 2 weeks IC medication as stop for cumulative dose calculation. In case 'IV or IM corticosteroids' is the ICE, use the first day of this IC medication as stop for cumulative dose calculation. In case 'very potent TCS for 7 consecutive days or 14 days in total' is the ICE, use the end of the 7 or 14 days IC medication as stop for cumulative dose calculation.

Details on the derivation of intercurrent events are provided in appendix 9.1.

A supplementary analysis for this secondary endpoint will use the 'treatment policy strategy' where the occurrence of the intercurrent event is considered irrelevant: NCOD is calculated regardless of whether or not the intercurrent event occurs.

Rescue therapies will not be considered for the NCOD endpoint since rescue therapies are only permitted after discontinuation of IMP treatment and NCOD calculation is restricted to the on IMP treatment period.

- 2) The proportion of participants that have achieved IGA-BP score of 0 while receiving efgartigimod PH20 SC or placebo and have been off OCS therapy for ≥8 weeks at week 36: the same approach for handling the main ICEs (composite strategy), for the handling of rescue therapies and for handling missing data, as suggested for the primary analysis, will be applied.
- 3) The proportion of participants that have achieved control of disease activity (CDA) while receiving efgartigimod PH20 SC or placebo and remain free of relapse through week 36: the same approach for handling the main ICEs (composite strategy), for the handling of rescue therapies and for handling missing data, as suggested for the primary analysis, will be applied.
- 4) The proportion of participants that have achieved CR while receiving efgartigimod PH20 SC or placebo and while receiving minimal OCS therapy for ≥8 weeks (CRmin) at week 36:

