11) Time from CRoff onset to Relapse, calculated only in participants with CRoff as the difference between the first date of relapse and the first date CRoff was achieved. Similar calculations and censoring rules are applied as for 'time from CDA to Relapse'.

Time from CR onset to Relapse will be analysed in a similar way as 'time to CRmin'.

- 12) NCOD as calculated for the different subperiods. NCOD from CDA/CR onset until relapse will only be analysed in participants with CDA/CR respectively. Same analysis will be performed as for the primary estimand of the key secondary parameter with ICEs handled according a 'while on treatment' strategy.
- COD will be calculated for the on IMP treatment period and the subperiods mentioned before. Only descriptive statistics will be presented.
- 13) Changes from baseline at week 36 in the 24-hour worst Itch NRS score will be analysed in the same way as for the 24-hour average itch score in the key secondary analysis.
- 14) Proportion of participants who received rescue therapy before week 36. A 'treatment policy' approach will be applied by ignoring main ICEs. Same CMH model as proposed for the primary endpoint.
- 15) ABQOL (17 items), EQ-5D-5L (5 dimensions) and DLQI (10 items) are assessed by the investigator at baseline, Week 12, Week 26 and at Week 36/ETD/ESD. Frequency tabulations will be provided for the percentages of participants within each outcome of QoL questionnaire items. Additionally cumulative percentages (starting with the best outcome result) will be calculated. A 'treatment policy' approach will be applied by ignoring main ICEs. For participants who received rescue therapy, only assessments prior to or on the start date of rescue therapy will be considered.
- 16) EQ-5D-5L VAS score and DLQI score are assessed by the investigator at baseline, Week 12, Week 26 and at Week 36/ETD/ESD. A total ABQOL score is calculated as the sum of all 17 items score 0 to 3 with higher score indicating worse condition. Missing items are imputed with the average score of the present items if at least half (9) of the items are present. The total score is rounded to the highest integer. A 'treatment policy' approach will be applied by ignoring main ICEs. For participants who received rescue therapy, only assessments prior to or on the start date of rescue therapy will be considered.

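### No planned steroid-dose analysis counts OCS taken after IMP stops, although the protocol endpoint runs to week 36; the NCOD denominator after an intercurrent event also needs fixing

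*SAP*

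**What the plan says.** Protocol 3.2 (Table 4) and 9.3.3.1 define key secondary endpoint 1 as the cumulative OCS dose from baseline to week 36. It is analysed by ANCOVA as a normalised cumulative OCS dose (NCOD), with weight and days in study as the normalisers. Protocol 9.3.3.1 leaves the handling of intercurrent events (ICEs) for the key secondary endpoints to the SAP.

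The SAP restricts the calculation to the on-IMP period:

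- SAP 3.5.2: "The denominator of the NCOD should cover all days on IMP treatment in the study, starting at baseline". Each NCOD period listed there ends at the end of the on-IMP period or at an earlier event.
- SAP 2.2.1, Table 1, ends the on-IMP period at "Last IMP administration date with 23:59 added as time part".
- SAP 4.1.3.1, while-on-treatment estimand: when intercurrent medication occurs, "stop calculating cumulative dose after ICE". Nothing is said there about the denominator.
- SAP 4.1.3.1, treatment-policy supplement: "NCOD is calculated regardless of whether or not the intercurrent event occurs". The next paragraph explains why rescue is not considered: "rescue therapies are only permitted after discontinuation of IMP treatment and NCOD calculation is restricted to the on IMP treatment period".
- SAP 4.1.4, item 12, for the unnormalised dose: "COD will be calculated for the on IMP treatment period and the subperiods mentioned before". That analysis is descriptive only.

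Protocol 7.1.1 keeps participants who stop IMP in the study to week 36, and Protocol 6.8.3 allows OCS among the rescue treatments.

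**The concern.** The tested NCOD depends on when IMP stops as well as on how much steroid is taken. On a tapering course, an early stop keeps the high-dose weeks and drops the low-dose ones, which raises NCOD. If OCS is raised again after IMP stops, truncation leaves that steroid out. A treatment-policy analysis would normally show whether this matters. Here it ignores intercurrent medication but keeps the same on-IMP window. The steroid-sparing endpoint is alpha-controlled in part B, and a reader will find no dose-based test close to the protocol's own endpoint to set beside it.

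The ICE rule is a second problem. If the numerator stops at the ICE and the denominator does not, a participant who takes a disallowed treatment appears to use less steroid per day. Two programmers could also derive different values for the same tested variable.

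**Working it through.** **Plan's own figure.** The worked conversion in SAP 3.5.2 reproduces: 12 mg methylprednisolone × 10 / 8 = 15 mg prednisone.

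**Inputs.** Study day = 7 × week + 1. The last planned dose at week 35 is day 246 and week 36 is day 253 (Protocol 1.3). Doses are for an 80 kg participant from Protocol Table 7. NCOD = (sum of daily mg / 80) / days in the period. The courses are illustrations; the documents do not say how common they are.

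**Completers.** 253 − 246 = 7 days uncounted; 7/253 = 2.8%.

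**General relation.** With last IMP dose on day T, week-36 NCOD = [T × on-IMP mean + (253 − T) × post-IMP mean] / 253. The week-36 value is therefore higher than the on-IMP value exactly when the post-IMP mean daily dose exceeds the on-IMP mean.

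**(a) Tapering course.** CDA at week 1, fastest taper: 40 mg × 21 days, then 22.5, 15, 10, 7.5, 5 and 2.5 mg × 14 days each = 840 + 875 = 1715 mg = 21.44 mg/kg, off OCS from day 106.

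| Last IMP day | Counted mg/kg | On-IMP NCOD | Days 1–253 |
|---|---|---|---|
| 246 | 21.44 | 0.087 | 0.085 |
| 141 | 21.44 | 0.152 | 0.085 |
| 85 | 20.63 | 0.243 | 0.085 |

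The same steroid course gives nearly a threefold spread. In an arm of 60, one day-85 stop moves the mean by (0.2426 − 0.0871)/60 = 0.0026. That is 3.0% of 0.087, which is a low base because it assumes that everyone else tapers at the fastest rate.

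**(b) Two relapses.** As (a) to day 77 (1610 mg). Relapse on day 78 returns to 10 mg × 21 days, then 7.5, 5 and 2.5 mg × 14 days each. The second relapse and the last IMP dose fall on day 141 (2.5 mg). Total 2032.5 mg; 2032.5/80/141 = 0.180. After that:

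- course (a) repeated: 3747.5/80/253 = 0.185, with 1 − 2032.5/3747.5 = 46% of the steroid uncounted;
- 40 mg held for days 142–253: 6512.5/80/253 = 0.322, with 1 − 2032.5/6512.5 = 69% uncounted.

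**(c) Treatment failure.** 40 mg × 21 days, then 60 mg; last IMP dose on day 36: 1740/80/36 = 0.604, with 217 days left out. If the post-IMP mean is assumed to be 0.2, 0.5 or 0.75 mg/kg/day, the value to day 253 is (21.75 + 217 × mean)/253 = 0.258, 0.515 or 0.729. Assumed averages are used because Protocol 6.8.1.3 starts tapering only after CDA has been sustained, so a taper straight from treatment failure would be outside the stated regimen.

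In (a) the on-IMP value is above the week-36 value; in (b) it is below. The sign can go either way.

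**(d) Denominator after an ICE.** Course (a) to day 84 is 1645 mg = 20.56 mg/kg. With IMP continued to day 246, 20.56/246 = 0.084; with the denominator ended at the ICE, 20.56/84 = 0.245. The ratio is 246/84 = 2.9. In general it is 246 divided by the ICE day: 4.3 at day 57, 2.5 at day 100 and 1.3 at day 183.

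**Other outputs.** The concomitant OCS table is by drug class and covers "all medications from the OCS CRF form, excluding OCS medications administered as rescue therapy". The rescue table in SAP 3.4.3 leaves out anything on the OCS form. Rescue OCS recorded on that form is therefore in neither table, and the dedicated OCS listing (16.2.5.2) is on-IMP only. The general therapy listing (16.2.4.4) and the rescue listing (16.2.4.7) do exist, but neither is a dose analysis.

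**The case against.** The protocol delegates ICE handling to the SAP, so a while-on-treatment estimand is a legitimate choice. The main ICEs for NCOD are intercurrent medications only, and the supplement ignores exactly those, so its label is consistent within the SAP. Both points stand, and for that reason the tested estimand should stay.

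A reader might infer that no planned test sees steroid use after IMP stops. The documents do not support that. SAP 4.1 treats stops for reasons other than lack of efficacy as still receiving IMP. Off-OCS or minimal-OCS status after such a stop therefore enters the week-36 CMH tests, rescue counts as non-response there, and rescue before week 36 has its own CMH test. Only a dose-based analysis is missing.

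A reader might also infer that the change of period was concealed. SAP 1.4.3.1, 3.5.2 and 4.1.3.1 state the on-IMP period openly, and SAP 6.1 prints a denominator of period duration in days. What 6.1 lacks is a statement that days in study became the on-IMP period, while Protocol 9.3.3.1 still says days in study.

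The examples are constructed, and in the milder version of (b) the normalised value hardly moves (0.180 against 0.185) although 46% of the steroid is uncounted. That is fair. Matching windows may also be the intended reading after an ICE, but SAP 3.5.2 as worded says otherwise.

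**Conclusion.** The point holds in this form. All planned dose-based OCS analyses end at or before the last IMP dose, and none corresponds to the protocol's baseline-to-week-36 endpoint. The loss is small for completers (2.8% of days) and can be large for an individual early discontinuer. It should not be read as bias in favour of either arm: the documents give no discontinuation rate, ICE rate or NCOD standard deviation, so the between-arm effect cannot be sized or signed, and no effect on the rejection rate is claimed.

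The ICE denominator is a definite drafting defect. Read literally, it understates the while-on-treatment NCOD after an ICE, by a factor of 1.3 to 4.3 in the examples. It affects only participants who take a disallowed treatment while on IMP, and their number is unknown.

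Both are worth correcting before part B is unblinded. The figures rest on an 80 kg participant, Table 7 doses and the stated courses.

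**What to change.** 1. Keep the while-on-treatment NCOD as the tested estimand, and keep the existing on-IMP treatment-policy supplement. Add a supplementary treatment-policy NCOD in the FAS, with descriptive statistics and the same ANCOVA, from first IMP to the week 36 visit. It should count OCS taken after IMP stops, after an ICE and as rescue. Adding it beside the on-IMP supplement changes one thing at a time, so any difference can be attributed to the window.
2. For death or study exit before week 36, divide by days in study to that date, which is the protocol's own normaliser. Give a fixed 253-day version as a sensitivity analysis, and state its assumption: dividing the observed dose by 253 treats the days after exit as steroid-free. Under SAP 3.5.2, if "no record exists in the CRF indicating OCS use that day, the dose will be assumed to be 0 mg"; limit this rule to days under observation.
3. In SAP 3.5.2 and 4.1.3.1, end the while-on-treatment denominator on the day the dose sum stops when an ICE occurs.
4. State in SAP 6.1 that the period changed from days in study, to week 36, to the on-IMP period.

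The cost is SAP wording, one extra derived variable and one extra set of tables. OCS monitoring is already scheduled to week 36. The week-36 version will reflect rescue treatment, so it does not isolate efgartigimod. OCS records may be sparser after IMP stops, because only the mandatory visits continue.
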